For the primary efficacy endpoint, a power calculation was performed for significance calculated by a two group t-test with a two-sided α of 0.05. Taking the standard deviation for the change in HbA1c to be 1%, a sample size of 128 in the bexagliflozin group and 64 in the placebo group is predicted to have 90% power to detect a difference between groups of 0.5% in mean HbA1c change. To account for an estimated drop-out rate of approximately 10%, a study design was adopted in which 140 subjects are planned to be randomized to the bexagliflozin group and 70 subjects to the placebo group. Statistical analyses and summaries will be performed using SAS[®] software (SAS Institute, Cary, NC).

LIST OF ABBREVIATIONS

ADA	American Diabetes Association
AE	adverse event
AIDS	acquired immunodeficiency syndrome
ALB	albumin
ALT	alanine aminotransferase
AST	aspartate aminotransferase
ATC	anatomic therapeutic chemical
BMI	body mass index
BUN	blood urea nitrogen
Ca	calcium
CEC	Cardiovascular Endpoint Committee
ConMed	concomitant medicines
CFR	Code of Federal Regulations
CI	confidence interval
Cl	chloride
CRF	case report form
CRO	contract research organization
CV	cardiovascular
DKA	diabetic ketoacidosis
dL	deciliter
DPP4	dipeptidyl peptidase-4
DSMB	data and safety monitoring board
ECG	electrocardiogram
eGFR	estimating glomerular filtration rate
FPG	fasting plasma glucose
GCP	Good Clinical Practice
GMI	genital mycotic infection
GLP-1	glucagon-like peptide-1
GGT	gamma glutamyl transferase
GMI	genital mycotic infection
HbA_{1c}	hemoglobin A1c
HBsAg	hepatitis B surface antigen
HCV	hepatitis C virus
Het	hematocrit
HDL-C	high density lipoprotein cholesterol
Hgb	hemoglobin
1150	nomogioum

HIV	human immunodeficiency virus
ICH	International Conference on Harmonization
IEC	independent ethics committee
IRAE	immediately reportable adverse event
	Institutional Review Board
IRB	
ITT	intention to treat
IWRS	Interactive Web Response System (IWRS)
K	potassium
LDL-C	low density lipoprotein cholesterol
LOCF	last observation carried forward
MACE	major adverse cardiovascular event
MCH	mean cell hemoglobin
MCHC	mean cell hematocrit
MCV	mean cell volume
MDRD	Modification of Diet in Renal Disease
MedDRA	Medical Dictionary for Regulatory Activities
MMRM	Mixed model repeated measurement
mg	milligram
MI	myocardial infarction
mL	milliliter
Na	sodium
NYHA	New York Heart Association
OHA	oral hypoglycemic agent

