9.5.1 Primary Efficacy Endpoint

The primary efficacy hypothesis is that bexagliflozin reduces HbA1c after 24 weeks of treatment when compared to placebo. The analysis of the change in HbA1c at week 24 will be based on ITT Analysis Set using all observed data and a mixed model repeated measures (MMRM) approach that will include terms for treatment, visit, treatment-by-visit interaction and randomization stratification factors as fixed effects and the baseline HbA1c value as a

fixed effect covariate. Least squares mean treatment differences between the bexagliflozin group and the placebo group at week 24 will be estimated from the model with the corresponding p-values and their two-sided 95 % CI presented. An unstructured covariance will be used to model the within-subject correlation. If the model with the unstructured covariance structure does not converge, an autoregressive(1) covariance structure will be used. HbA1c values obtained after the start of rescue medication will not be excluded from the analysis.

Sensitivity analyses will be performed as:

- 1. A multiple imputation method will be used to impute missing observations (including observations obtained after rescue medication) in the ITT Analysis Set prior to carrying out the MMRM analysis.
- 2. A multiple imputation method will be used to impute missing observations (not including observations obtained after rescue medication) in the ITT Analysis Set prior to carrying out the MMRM analysis.
- 3. A last observation carried forward (LOCF) method will be used to impute the missing observations in the ITT Analysis Set prior to carrying out the MMRM model.

For supportive analyses, the primary efficacy endpoint will be analyzed with observed available data using the PP analysis set in a similar manner as above.

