3.6. DETERMINATION OF SAMPLE SIZE

Approximately 210 subjects will be randomized 2:1 to bexagliflozin tablets, 20 mg or bexagliflozin tablets, placebo. The sample size calculation for this study was based on a two group t-test with a two-sided significance test at the 5% level and the following assumptions:

- 1. The difference in mean change from baseline to week 24 in HbA1c in the bexagliflozin group compared to that of the placebo group will be -0.5%.
- 2. The standard deviation for the difference in mean change from baseline to week 24 in HbA1c between the bexagliflozin group and the placebo group will be 1.0%.

Under the above assumptions, an estimated sample size of 128 and 64 evaluable subjects in the bexagliflozin and placebo arms, respectively, yielded a 90% power that bexagliflozin treatment will be found to be significantly different from placebo. To account for an estimated drop-out rate of approximately 10%, the study design anticipates randomizing 140 and 70 subjects in the bexagliflozin and placebo arm, respectively.

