This hypothesis will be tested based on ITT analysis set using all observed data and a mixed model repeated measures (MMRM) approach. The MMRM model will include terms for background anti-diabetes treatment status (treatment naïve or not), treatment, visit, treatment-by-visit interaction and the baseline HbA1c value as a fixed effect covariate. Country will be used as a fixed effect if pooling by country is used. The analysis will evaluate the mean change from baseline in HbA1c over the 24-week double-blind treatment period. An unstructured covariance will be used to model the within-subject correlation. The Kenward-Roger approximation will be used to estimate denominator degrees of freedom. If the model with the unstructured covariance structure does not converge, an autoregressive(1) covariance structure will be used. HbA1c values obtained after the start of rescue medication will not be excluded from the analysis.

Based on the MMRM model, the treatment and treatment-by-visit interaction terms allow for comparisons of the treatment groups at each visit, and over week 6 to week 24. Least squares (LS) mean treatment differences between the bexagliflozin group and the placebo group at week 24 will be estimated from the model with the corresponding p-values and their two-sided 95 % CIs presented. Sample SAS code will be provided in Appendix 1.

Descriptive statistics (n, mean, Q1, median, Q3, SD, minimum, and maximum) will be reported by treatment group and visit, along with the least squares means, differences

1007728

between LS means, a 2-sided 95% confidence interval for each difference, p-values from the model effects. In addition, the LS means with standard errors of the change from baseline over time and difference between treatment groups with 95% will be presented graphically for the ITT population.

For supportive analyses, the primary efficacy endpoint will be analyzed with observed available data using the PP analysis set in a similar manner as above.

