8.2.1. Key secondary efficacy endpoints and analyses

A hierarchical testing procedure will be applied to these endpoints in the sequence provided above. These key secondary endpoints will only be tested sequentially when significant treatment differences are established for the primary efficacy endpoint in the comparisons between the bexagliflozin and placebo groups.

Analysis for key secondary endpoints will be based on the ITT analysis set and repeated for the PP analysis set. The sensitivity analyses stated in Section 8.1.2 will be performed on all key secondary endpoints.

8.2.1.1. Change in SBP from baseline to week 24

This will be tested if the primary efficacy endpoint is significant. Change from baseline in sitting SBP at week 24 will be analyzed using the MMRM ANCOVA model with unstructured covariance assumption. The model will include terms for treatment, visit, treatment-by-visit interaction, baseline HbA1c and background anti diabetes treatment status as fixed effects and the corresponding baseline SBP value as an additional fixed effect covariate. Treatment comparison p-values and difference at week 24 will be estimated from the model, with the two-sided 95% CIs of the treatment difference also presented. If the model does not converge with the unstructured correlation assumption, an autoregressive (1) model will be used.

1007728

8.2.1.2. Change in body weight from baseline to week 24 in subjects with a BMI ≥ 25 kg/m²

This will be tested if the primary efficacy endpoint and the key secondary endpoint-change from baseline SBP are significantly different between bexagliflozin and placebo groups based on ITT analysis set. The comparison of change in body weight between randomized treatments at week 24 will be carried out using the ANCOVA model. The model will include terms for treatment, background anti diabetes treatment status and baseline HbA1c as fixed effects, and the corresponding baseline weight value as an additional fixed effect covariate. Treatment comparison p-values and difference at week 24 will be estimated from the model, with the two-sided 95 % CIs of the treatment difference also presented. If the primary hypothesis is not significant, the nominal p-value will not be used for inferential purposes.

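### The primary MMRM imposes one baseline HbA1c slope at all four visits; a baseline-by-visit term is an optional, nearly free gain in precision at Week 24

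*SAP*

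**What the plan says.** The primary model in SAP 8.1.1 lists background treatment status, treatment, visit, treatment-by-visit, and "the baseline HbA1c value as a fixed effect covariate", with country added if pooling by country is used. Covariance is unstructured, with AR(1) as the fallback. Protocol 9.5.1 lists "treatment-by-visit interaction and randomization stratification factors as fixed effects" plus the baseline HbA1c value. Neither text crosses baseline, or the stratification factors, with visit.

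The estimate of interest is the least squares mean difference at Week 24. SAP 8.1.2 reuses this MMRM on each multiply imputed dataset. Sample code is deferred to Appendix 1, which is not in the text available for review. SAP section 12 declares no change from the protocol analysis.

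**The concern.** Treatment effects may differ by visit in this model, but the dependence of change on baseline may not. The documents give some reason to expect that dependence to grow:

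- Protocol 3.3.1 says HbA1c reflects glycaemia over 2 to 3 months. Week 6 lies inside that window and Week 24 well beyond it.
- Rescue thresholds tighten during treatment (protocol 3.2.3.4) and post-rescue values stay in the primary analysis. Subjects with high baseline values may therefore be pulled down more at later visits. This is an inference, since no slopes are given.

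The SAP's own imputation does not assume a common slope. The regression step in SAP 8.1.2 fits a separate model at each time point, with baseline among the predictors. The completed data then go into the more restrictive analysis model.

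If the slopes differ, an unstructured fit weights the common slope towards the less variable visits. When the SD of change grows over time, these are the early ones. The misfit at Week 24 is absorbed as residual variance, and the reported interval for the primary comparison widens.

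**Working it through.** **1. The plan's own figure.** The calculation is a "two group t-test with a two-sided significance test at the 5% level" with difference 0.5, SD 1.0 (protocol synopsis: "Taking the standard deviation for the change in HbA1c to be 1"%) and 2:1 allocation.

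- Placebo n = (1.960 + 1.282)² × (1 + 1/2) × 1.0² / 0.5² = 63.04, rounded up to 64, with 128 on bexagliflozin. This matches the plan.
- SE = 1.0 × √(1/128 + 1/64) = 0.1531. Power = Φ(0.5/0.1531 − 1.96) = 0.904, or 0.901 by noncentral t.
- At 10% dropout from 140/70, 126/63 remain, with power 0.900.

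The stated 90% is reproduced. It uses no baseline adjustment.

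**2. Formula for the common slope.** For an unstructured MMRM with complete data and a large sample, let β hold the true visit slopes and S the residual covariance. The fitted common slope tends to

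b = (1′S⁻¹β) / (1′S⁻¹1),

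and the Week 24 model SE ratio (common slope / slope by visit) is

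√[1 + Var(baseline) × (β₂₄ − b)² / residual variance at Week 24].

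This is never below 1, and equals 1 when b = β₂₄.

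**3. Assumptions, none given in the documents.** Baseline SD is 0.8 or 1.0. The total SD of change is fixed at the plan's 1.0 at Week 24 and is either 1.0 at every visit or grows as 0.6, 0.8, 0.9, 1.0. Several residual correlation patterns were used.

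**4. Worked example.** Slopes are −0.20, −0.35, −0.45, −0.50; baseline SD 0.8; serial correlation 0.8. The Week 24 residual variance is 1 − 0.5² × 0.8² = 0.84, so the by-visit SE is √0.84 × 0.1531 = 0.1403.

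- Growing SD: b = −0.219. Ratio = √(1 + 0.64 × 0.281² / 0.84) = 1.030, giving SE 0.1445.
- Equal SD: b = −0.381. Ratio = √(1 + 0.64 × 0.119² / 0.84) = 1.005, giving SE 0.1411.

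**5. Range of Week 24 SE ratios.**

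| Slope, week 6 to week 24 | Equal SD | Growing SD |
|---|---|---|
| constant −0.4 | 1.000 | 1.000 |
| −0.2 to −0.5 | 1.003–1.007 | 1.030–1.060 |
| −0.1 to −0.7 (extreme) | 1.000–1.017 | 1.108–1.202 |

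A smaller change, −0.20 to −0.40 with residual SDs growing from 0.60 to 0.90, gave a simulated ratio of 0.1392/0.1370 = 1.016. In every growing-slope scenario, power with the common slope was at least 0.918, against 0.904 for the planned unadjusted comparison.

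**6. Simulation.** Each scenario had 500 trials of 210 subjects at 2:1, with randomization stratified on HbA1c and background status, baseline SD about 0.74, about 11% missing at Week 24, and dropout depending on baseline and arm.

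| Slopes | SD of change | Model SE ratio | Empirical SD ratio | Mean estimate, common / by visit (true −0.5) |
|---|---|---|---|---|
| −0.2 to −0.5 | growing | 1.027 | 0.998 | −0.508 / −0.503 |
| −0.2 to −0.5 | equal | 1.007 | 1.000 | −0.508 / −0.505 |
| −0.1 to −0.7 | growing | 1.098 | 1.021 | −0.510 / −0.507 |
| −0.1 to −0.7 | equal | 1.025 | 1.023 | −0.506 / −0.500 |
| constant −0.4 | growing | 1.001 | 0.999 | −0.496 / −0.496 |

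Without HbA1c stratification, the two growing-SD, growing-slope cases gave empirical SD ratios of 1.021 and 1.073. Stratification narrows the gap because, under an assumed truncated normal baseline, only about a third of the baseline variance (32–36%) lies within strata.

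**The case against.** A single baseline covariate is a valid prespecified choice, and the size of any loss depends wholly on quantities the documents do not give. With equal SDs and moderate slope changes the loss is below 1%. Extreme slope patterns are hard to defend: change is post-treatment minus baseline, so measurement error in baseline alone makes the slope negative at every visit, including week 6. All of this stands, and it limits the point to a refinement.

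Stratified randomization already balances baseline HbA1c between arms, so the estimator itself is almost as precise with a common slope. This also stands. A reader might square the SE ratio and call the loss an equivalent number of extra subjects. That does not follow, because the model SE rises more than the true sampling variability does. What remains is mostly an interval that is slightly too wide.

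The Appendix 1 code could already contain the interaction, and this cannot be checked. If it does, the text of SAP 8.1.1 still needs to agree with it.

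The objection does not remove the asymmetry: the extra term costs essentially nothing if the slopes are equal and tightens the reported interval if they are not.

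**Conclusion.** The point holds as an optional precision improvement for the HbA1c analysis. Both model descriptions impose one baseline slope. If the true slope grows over time, the reported Week 24 SE is too large: by about 0–1% with equal SDs and moderate slope changes, about 1–6% if the SD of change grows, and more only with extreme slope changes. The corresponding change in true sampling variability is about 0–2%. These sizes rest on assumed slopes, visit SDs, correlations and baseline SD.

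Three stronger readings are not supported:

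- *Bias under glycaemia-related dropout.* Common-slope estimates averaged −0.495 to −0.510 over all simulated scenarios against a true −0.5. In the tabulated scenarios they differed from the by-visit estimates by at most 0.006.
- *An underpowered or invalid primary test.* The sample size uses an unadjusted t-test, and the common-slope model was more precise than that in every scenario. The error is a wide interval, so type I error is not at risk.
- *The same defect in the blood pressure model.* SAP 8.2.1.1 also enters "the corresponding baseline SBP value as an additional fixed effect covariate" without a visit interaction, but the 2-to-3-month argument is specific to HbA1c and nothing was computed for SBP.

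**What to change.** Add a baseline HbA1c-by-visit term to the primary MMRM in SAP 8.1.1 and to the same MMRM applied after multiple imputation in SAP 8.1.2. Make the Appendix 1 code match. Record the added term in SAP section 12, because protocol 9.5.1 does not contain it and section 12 now reports no change. Do this before unblinding, so that the term cannot look data-driven.

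The cost is a few lines of SAP text and three degrees of freedom (four slopes instead of one) in about 210 subjects. With equal slopes, the simulated SE was essentially unchanged (ratio 1.001).

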9.6 Secondary Efficacy Endpoints

9.6.1 Key secondary Efficacy Endpoints

The key secondary efficacy endpoints include:

- Change in SBP from baseline to week 24
- Change in body weight from baseline to week 24 in subjects with a BMI \ge 25 kg/m²

A hierarchical testing procedure will be applied to these endpoints in the sequence provided above. These key secondary endpoints will only be tested sequentially when significant treatment differences are established for the primary efficacy endpoint in the comparisons between the bexagliflozin and placebo groups.

The comparison between randomized treatments at week 24 in SBP will be carried out using the MMRM ANCOVA model with unstructured covariance assumption. The model will include terms for treatment, visit, treatment-by-visit interaction, and randomization stratification factors as fixed effects and the corresponding baseline SBP value as an additional fixed effect covariate. Treatment comparison p-values and the least square mean difference at week 24 will be estimated from the model, with the two-sided 95 % CIs of the difference also presented. If the model does not converge with the unstructured correlation assumption, an autoregressive(1) model will be used.

Change from baseline in body weight at week 24 will be analyzed using ANCOVA method.

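### If the unstructured model fails to converge, the one-step AR(1) fallback can make the Week 24 HbA1c test anti-conservative when variance rises over visits; the size depends on visit SDs the documents do not give

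*SAP*

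**What the plan says.** SAP 8.1.1 fits an MMRM to HbA1c change at Weeks 6, 12, 18 and 24 with an unstructured covariance and Kenward-Roger denominator degrees of freedom, and tests the Week 24 difference. If that model does not converge, "an autoregressive(1) covariance structure will be used". The protocol synopsis and Protocol 9.5.1 have the same single-step rule.

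The SBP model repeats it. Protocol 9.6.1 says "an autoregressive(1) model will be used", and SAP 8.2.1.1 says "an autoregressive (1) model will be used".

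Neither document names a heterogeneous structure, an intermediate step or an empirical (sandwich) variance. SAP 8.1.1 refers to sample code in Appendix 1, which is not in the text available for review.

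The only SD for HbA1c change is in SAP 3.6 and Protocol 9.2: "HbA1c between the bexagliflozin group and the placebo group will be 1.0", in percentage points, for change to Week 24. No SD is given for Weeks 6, 12 or 18.

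**The concern.** A plain AR(1) structure has two parameters: one variance shared by all visits and one correlation. The tested contrast sits at the last visit. If HbA1c change is less variable at Week 6 than at Week 24, the shared variance falls below the Week 24 variance, and the Week 24 standard error is too small. Kenward-Roger does not repair this, because it is a small-sample adjustment made under the assumed covariance form.

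Some growth is plausible. Protocol 3.3.1 notes that HbA1c reflects control over 2 to 3 months, so the Week 6 value captures only part of the response to treatment.

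The primary test also gates the key secondary hierarchy. A fallback that errs towards rejection would weaken the 5% familywise control stated in Protocol 9.1.1, in exactly the circumstance for which the rule was written.

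**Working it through.** **1. The plan's own figure.** SAP 3.6 uses a "two group t-test with a two-sided significance test at the 5% level" with a difference of 0.5, an SD of 1.0 and 2:1 allocation.

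- Placebo n = (1 + 1/2) × (1.960 + 1.282)² × 1.0² / 0.5² = 63.04, so 64, with 128 on bexagliflozin.
- SE = √(1/64 + 1/128) = 0.153. Normal-theory power = Φ(0.5/0.153 − 1.96) = 0.904; the t-test gives 0.901.

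The stated 90% power at 128 and 64 reproduces. The documents give no type I error for the fallback.

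**2. Large-sample type I error under plain AR(1).** With complete data and a treatment effect at each visit, the Week 24 contrast has true standard error SD₂₄ × √(1/n₁ + 1/n₂). The fitted model reports σ_AR × √(1/n₁ + 1/n₂), where σ_AR is the SD from the AR(1) matrix V that best fits the true covariance Σ (it minimises log|V| + tr(V⁻¹Σ)). Hence

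α = 2 × [1 − Φ(1.96 × σ_AR / SD₂₄)].

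Week 24 SD is 1.0 (from the documents). The earlier SDs are **assumed**, linear from Week 6 to Week 24, with true lag-one correlation 0.8.

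| Week 6 SD (assumed) | σ_AR | α, large sample | α, simulated |
|---|---|---|---|
| 1.2 (falling) | 1.10 | 0.031 | not run |
| 1.0 (constant) | 1.000 | 0.050 | 0.057 |
| 0.9 | 0.951 | 0.062 | 0.070 |
| 0.8 | 0.904 | 0.076 | 0.080 |
| 0.7 | 0.860 | 0.092 | 0.089 |
| 0.6 | 0.819 | 0.109 | 0.110 |
| 0.5 | 0.781 | 0.126 | 0.121 |

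Worked row, Week 6 SD 0.6:

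- The visit SDs are 0.600, 0.733, 0.867 and 1.000. The root of the mean variance is √[(0.360 + 0.537 + 0.752 + 1.000)/4] = 0.814, close to the fitted 0.819.
- At 128 and 64 subjects the reported SE would be 0.819 × 0.153 = 0.125 against a true 0.153.
- 1.96 × 0.819 = 1.605, so α = 0.109.

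An early rise and then a plateau (0.6, 0.85, 0.95, 1.0) gives 0.097, or 0.094 simulated. The results barely change for AR correlations of 0.7-0.9 or compound-symmetric correlations of 0.6-0.8.

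**3. Simulation.** Each scenario had 2,000 null trials with 140 and 70 subjects, four visits, 10% completely random dropout, a baseline covariate and REML AR(1) with model-based errors. Monte Carlo SE is about 0.005-0.007. Kenward-Roger was not coded; fixed degrees of freedom were used, and taking 190 instead of 600 changed no result by more than 0.0025.

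**4. What doubling requires.** α = 0.10 needs σ_AR/SD₂₄ = 1.645/1.96 = 0.839. That lies between the rows for Week 6 SD 0.7 and 0.6, which is an SD rise of 1/0.7 = 1.4-fold to 1/0.6 = 1.7-fold.

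**5. Alternatives.**

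- Heterogeneous AR(1), large sample: Week 24 SD recovered as 1.000 and α = 0.050 in every scenario checked, including compound-symmetric truth.
- Plain AR(1) with sandwich errors, same simulations: 0.040-0.050.
- Unstructured, 500 of the trials per scenario: 0.038-0.050.

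**The case against.** **The trigger is remote.** An unstructured matrix for four visits has 4 × 5/2 = 10 parameters, and about 210 subjects should support it. The documents give no probability of failure. This stands, and it keeps the point minor.

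**The text does not say equal-variance or model-based.** The Appendix 1 code could specify a heterogeneous form or a different standard error. This stands as a limit: the reading is the ordinary one for these words together with Kenward-Roger, but it is an inference.

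**Growth in variance is not documented.** Only the Week 24 SD is given. One design feature could work against growth: post-rescue HbA1c values stay in the primary analysis, and the suggested rescue thresholds in Protocol 3.2.3.4 fall from 270 to 240 to 200 mg/dL, which may pull in high late values. This also stands. It is why the result is a range that includes no inflation and conservatism.

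**SBP.** A reader might infer that the SBP test is inflated too, since the fallback wording is the same. The documents give no SBP SD at any visit and no SBP calculation was made, so that inference is not supported.

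None of this answers the remaining point: a rule written for the case where the planned model fails should hold its level over plausible variance patterns, and plain AR(1) with model-based errors does not.

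**Conclusion.** The concern holds in a conditional form. It needs three things together: non-convergence of the unstructured model, AR(1) read as homogeneous with model-based errors, and a variance of HbA1c change that rises to Week 24. The Week 24 type I error is then about 6% to 13% for a Week 6 SD of 0.9 down to 0.5, against a nominal 5%.

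Two stronger readings are tempting. One is that the fallback roughly doubles the type I error whenever variance grows. It does so only if the SD rises about 1.4- to 1.7-fold from Week 6 to Week 24, and nothing in the documents establishes that. The other is that the primary analysis itself is anti-conservative. It is not: the unstructured fit held its level in the simulations. This is a low-priority improvement to a contingency rule.

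**What to change.** In SAP 8.1.1, the protocol synopsis and Protocol 9.5.1, replace the single AR(1) step by an ordered list, moving to the next structure only on non-convergence:

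1. Unstructured, with Kenward-Roger.
2. Heterogeneous Toeplitz, with Kenward-Roger.
3. Heterogeneous AR(1), with Kenward-Roger.
4. If homogeneous AR(1) is kept as the last step, empirical (sandwich) standard errors with a named degrees-of-freedom method such as between-within.

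The heterogeneous structures come first because sandwich errors correct only the standard error. With dropout that depends on observed values, the point estimate still leans on the covariance form, and the simulations used completely random dropout. Heterogeneous Toeplitz was not itself simulated; it also has a separate variance for each visit, and it contains heterogeneous AR(1) as a special case.

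Use the same wording for SBP in SAP 8.2.1.1 and Protocol 9.6.1 for consistency only. Record the change in SAP section 12, which now reports no departure from the protocol's analysis. Make it before unblinding.

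The cost is a few more lines of text and slightly wider intervals if the fallback is used. Data collection, sample size and conduct do not change.
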